The intervention addresses the main UTBC factors influencing the intention and implementation of regular medicine taking. Items from standard UTBC scales (Ajzen et al. 1981) will assess the relevance of pre-intention factors and items from the validated Adolescent and Parent Medication Barriers Scales (Simons et al. 2007; Simons et al. 2010) to assess the relevance of implementation factors (see **Measurement**). After this assessment battery is collected from adolescents and parents, automated algorithms identify and recommend the specific intervention components tied to UTBC factors that are most relevant to address the needs of each adolescent/parent.

We will send weekly text message reminders to parents in the intervention group with prompts to use the new features on the mehealth for ADHD website. These messages will highlight a new intervention tool each week with a subject specific URL to take the parent

directly to the tool. The parent will receive different text message prompts depending on what tools were recommended and have been used.

We will also call parents in the intervention group to understand their experience with using the mehealth for ADHD website. The parent will be asked different questions depending on their level of engagement with the website. We will additionally ask about how their child is managing school and their ADHD symptoms. The phone call will take place as a semi-structured interview.

Intervention components targeting UTBC pre-intention factors

1. **Education** (Targeting **adolescent and parent** expectations, self-concept, affect and emotions)

The intervention delivers education about relevant topics (e.g. the etiology of ADHD; how medicine works; the importance of medication titration, how to mitigate side effects and minimize dosing regimen complexity, and how adolescents, parents, and doctors can work together to titrate medicine, conduct a trial on/off, and discourage diversion).

2. **Pediatrician supervised medication management** (Targeting **adolescent and parent** expectations, self-concept, affect and emotions).

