15. Client Satisfaction Questionnaire (CSQ) (Attkisson et al. 1982) is an 8-item unidimensional measure of client satisfaction with services. Psychometric properties, operating characteristics, and coefficient alpha (.93) are very strong for this measure which we will collect from adolescents and parents.
16. Decision Making Involvement Scale (DMIS) (Miller et al., 2012): is a 30-item scale to measure adolescent involvement in a decision. The five subscales are: “Child Seek” (child asks for an opinion or information from parent), “Child Express” (child expresses an opinion or information to parent), “Parent Seek” (parent expresses advice or opinion to child), “Parent Express” (parent expresses advice or opinion to child), and

“Joint/Options” (negotiation or brainstorming between parent and child). We will collect this measure from adolescents and parents.

DATA ANALYSIS

Hypothesis testing:

Each hypothesis examines part of the mechanism underpinning intervention impact on medication continuity.

Hypothesis #1: *Adolescents will use greater than 80% of relevant intervention components.* For each subject in the intervention group, we will calculate the proportion of **recommended** intervention components that were utilized by the subject during the study. The mean and 95% confidence interval (CI) will be computed to give a range estimate of the fidelity measure. To evaluate our hypothesis, we will utilize the computed CI to determine if 80% or greater is a plausible value, such that if the CI includes a value of 80% or greater we will reject the null hypothesis. We will also examine the temporal distribution of use for each of the recommended components.

Hypothesis #2: *Use of the intervention components will be related to improvements in the targeted UTBC factors.* Using a generalized linear model, we will test whether the intervention addressed the UTBC factors (i.e., pre-intention factor scales and ABMS/PBMS total and subscale scores). Model predictors will include a fixed effect indicator of time point (baseline or end of study). A significant effect of time point in the expected direction would indicate UTBC factor improvement.

Hypothesis #3: *Medication continuity will be higher in the intervention group compared to the control group.* We will compare the percentage of days covered with medicine using a two-sample t-test.

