Official Title of the study: **Randomized Controlled Trial of Web Based Tools to Improve Medication Continuity in Adolescents With ADHD**

NCT number: **NCT04386096**

Document name: **Statistical Analysis Plan**

Date of the document: **12/15/2021**

The results of the Web Based Tools study will be assessed as described in this document. This statistical analysis plan begins with an overview of the key components of the study, including its design, objectives, and outcomes measures. This is followed by a detailed description of the statistical analyses that will be utilized to address study hypotheses.

**1. Overview of study:** This study used a parallel group randomized control trial to test whether an intervention engages the proposed mechanism underlying medication continuity and improves outcomes. Adolescents and their parents that agreed to participate in the study were randomized to receive either the intervention (MeHealth for ADHD software with medication continuity tools) or the control group (MeHealth for ADHD software with no medication continuity tools). We used a stratified randomization procedure to ensure that the intervention and control groups were balanced with respect to the number of days covered with ADHD stimulant medication in the past year based on dispensing data. We planned to enroll a total of 44 adolescents aged 11-15 with ADHD with poor medication continuity from Cincinnati Children's Pediatric Primary Care Clinic (PPCC) in order to retain  $\geq 36$  subjects needed based on our sample size calculation.

**1.1 Study Objective:** Test a multi-component intervention that systematically identifies and targets aspects of the Unified Theory of Behavior Change (UTBC) model most relevant for each adolescent with poor ADHD medication continuity.

Working hypothesis 1: compared to the control group, the intervention group will have greater medication continuity as measured by number of days covered with medicine at the end of the study.

Working hypothesis 2: compared to the control group, the intervention group will have improved outcomes as measured by change in the Unified Theory of Behavior Change factors.

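### Protocol Hypothesis 2 claims a link between component use and UTBC factor improvement but is judged on a time effect with no use term or arm contrast, and the paired t-test in the SAP does not repair this

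*Protocol*

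**What the plan says.** Protocol, DATA ANALYSIS, Hypothesis #2 states: "Use of the intervention components will be related to improvements in the targeted UTBC factors". The model is a generalized linear model meant to show whether the intervention addressed the factors. Its outcomes are listed as "i.e., pre-intention factor scales and ABMS/PBMS total and subscale scores". On predictors it says "Model predictors will include a fixed effect indicator of time point (baseline or end of study"), and on the criterion: "A significant effect of time point in the expected direction would indicate UTBC factor improvement". It does not say which arm or arms enter the model.

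Protocol, Intervention, describes how components are assigned. "Items from standard UTBC scales (Ajzen et al. 1981) will assess the relevance of pre-intention factors". For the implementation factors, the plan relies on "items from the validated Adolescent and Parent Medication Barriers Scales". From these answers, "automated algorithms identify and recommend the specific intervention components tied to UTBC factors that are most relevant". No cut-off is given. Protocol, Outcome measures, items 10 and 12, name the same instruments as outcomes. Item 9 defines use for each participant as the share of recommended components completed.

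SAP 1.1, Working hypothesis 2, is a between-arm claim: "compared to the control group, the intervention group will have improved outcomes as measured by change in the Unified Theory of Behavior Change factors". SAP 2.3.3 says the arms will be compared on change in the pre-intention factors, intention and both barriers scales, and names a paired t-test each time. SAP 2.3.4 reports fidelity only as a mean and range, in the intervention group.

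**The concern.** The hypothesis is about use, but the criterion is about time. A time effect shows that scores moved between two dates. It does not show that they moved because of the tools, or that they moved more in participants who used them. Under Protocol, STUDY DESIGN, the intervention starts just before the school year and the trial ends four months later, so time point is also season. Repeat measurement is a further shared cause. A randomised control arm is available to remove such effects, and the named model does not use it.

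Protocol, Scientific Rigor, says the trial will address whether the intervention engages its mechanism and so merits a larger trial. Hypothesis 2 is part of that evidence. A positive result produced by calendar time would be reported as engagement of the mechanism.

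**Working it through.** **1. The plan's own figure.** The only sample size given is for days covered (Protocol, Power and Sample Size: difference 15.7, SD 16.5, two-sided 0.05, 80% power). The normal formula gives n = 2 × (1.960 + 0.842)² × (16.5/15.7)² = 2 × 7.849 × 1.1045 = 17.3, so 18 per group, as stated. The exact t solution is 18.35, and power at 18 is 79.2%. No power is stated for Hypothesis 2. Only n = 18 is carried forward.

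**2. Claim against test.**
- Claimed: use is related to improvement. Needed: a use term. Named: time point only.
- Implied: the intervention caused the change. Needed: an arm contrast. Named: none.
- Use is measured (Outcome measures, item 9), but neither document relates it to factor change. Hypothesis #4 relates factor change to medication continuity, not to use. SAP 2.3.4 is descriptive.

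**3. A change shared by both arms, with no effect of the tools.** For a paired test with n = 18 and scores in SD units, the SD of change is √(2(1 − r)) and the noncentrality is shift × √18 / SD of change. The critical value is t(0.975, 17) = 2.11. The shift (0.2 to 0.3 SD) and the pre-post correlation r are assumptions.
- r = 0.5: SD of change 1.00, noncentrality 0.85 to 1.27, favourable result in 12% to 22%.
- r = 0.7: SD 0.775, noncentrality 1.10 to 1.64, 18% to 34%.
- r = 0.9: SD 0.447, noncentrality 1.90 to 2.85, 43% to 77%.

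The nominal rate is 2.5%. This route needs no selection of factors.

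**4. Regression to the mean, conditional on selection.** If a factor is analysed because its baseline score was low, the expected spurious gain is (1 − r) × the mean depth of the selected baseline scores. For the lowest of five independent factors that depth is 1.163 SD, so the gain is 0.58, 0.35, 0.23 and 0.12 SD at r = 0.5, 0.7, 0.8 and 0.9. The table gives simulated favourable rejection rates with no true change (4,000 trials per setting, 18 per arm, normal scores).

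| r | No selection | Flagged below median (about 9 of 18) | Flagged in lowest third (about 6 of 18) | Each participant's worst of 5 | Worst of 5, pairing ignored |
|---|---|---|---|---|---|
| 0.5 | 2.3% | 20.0% | 23.8% | 71.2% | 56.8% |
| 0.7 | 2.5% | 13.7% | 15.0% | 46.8% | 18.0% |
| 0.8 | 2.6% | 10.3% | 11.2% | 32.0% | 4.6% |
| 0.9 | 2.4% | 6.2% | 7.9% | 17.7% | 0.2% |

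Trials with fewer than three flagged participants in either arm were dropped (251 of 4,000, about 6%, in the lowest-third setting at r = 0.5). The protocol gives internal consistency of 0.7 to 0.9 for the factor scales, but no four-month test-retest correlation, so r is an assumption.

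**5. The same settings with a between-arm test of change,** applying the same selection rule in both arms: 2.2% to 2.9% throughout. The Monte Carlo standard error near 2.5% is √(0.025 × 0.975/4000) = 0.25 points, so this agrees with the nominal rate.

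**6. The SAP test.** A paired t-test needs two values on the same unit. The two arms contain different participants, and no matching is described. The only pairing available is baseline with end of study, and that is the uncontrolled comparison again.

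**The case against.** The strongest reply is that the SAP is the later document, says results will be assessed as it describes, and states its only UTBC factor hypothesis as a between-arm comparison. On that view the missing control has been dealt with. This has weight, because the intention is clearly comparative. It does not settle the matter, because the test named cannot carry out that comparison, and the SAP neither mentions nor withdraws Protocol Hypothesis 2. It also adds no analysis of use.

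The list of predictors may not be exhaustive, and Hypothesis 2 does not say that the control arm is left out. Both are true. But the criterion rests on the time term alone. Extra covariates, or both arms pooled under one time effect, would still give no arm contrast.

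A reader might infer that regression to the mean alone will confirm Hypothesis 2. The documents do not support that. The hypothesis speaks of targeted factors, but the outcomes listed are whole scales, including totals, with no restriction to each participant's targets. Without selection there is no inflation (2.3% to 2.6%). Nor do the documents say that targets are the worst scores. Two triggers that are described work otherwise: interest in a change of medicine or dose, and doubt about continued need in a teenager who is doing well. That the targeting answers and the baseline outcome scores come from one administration is a strong inference, not a statement.

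A reader might also infer that Hypothesis 2 decides whether a larger trial follows. The protocol gives it no such sole role. Each hypothesis is said to examine one part of the mechanism.

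Finally, the size and direction of any calendar effect on these scales are unknown. That stands, and it is why step 3 is a range over assumed values.

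**Conclusion.** The concern holds. As written, Hypothesis 2 is not tested: its model names no use term, and its criterion can be met by any favourable change common to both arms. The SAP points toward the right comparison but names a test that cannot make it, and leaves two unreconciled accounts of how UTBC factor change will be judged.

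For a shared shift of 0.2 to 0.3 SD, the favourable rate is 12% to 77% over correlations of 0.5 to 0.9. Regression to the mean is a further risk only if the analysis is restricted to factors targeted for poor baseline scores. It then gives about 18% to 71% for each participant's worst of five factors, and about 6% to 24% for participants flagged low on one factor. These rates assume a paired analysis, normal scores and, for the worst-of-five case, independent factors. An analysis that ignores pairing gives 0.2% to 57% for worst of five.

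This should be fixed. It is not critical to the trial, because the primary comparison of days covered does not depend on it.

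**What to change.** 1. Replace the time-effect test in Protocol Hypothesis 2, and the paired t-test for the UTBC factors in SAP 2.3.3, with one between-arm contrast: end-of-study score on arm plus baseline score, or a two-sample comparison of change. State which scales are analysed. If only targeted factors are, run the same targeting algorithm on baseline answers in both arms, so that selection and calendar effects cancel.
2. For the claim about use, report the association of the fidelity proportion with factor change within the intervention arm, labelled exploratory because use is not randomised.
3. Delete the criterion that reads a time-point effect as factor improvement due to the intervention, and say in the SAP how Hypothesis 2 relates to Working hypothesis 2.

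The cost is a dated SAP amendment and a few lines of code. The planned between-arm change scores already need both arms' surveys. Applying the algorithm to controls needs their baseline answers to have been kept.

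The downside is a lower chance of a significant result. With an assumed true effect of 0.5 SD, r = 0.7 and 18 per arm, the SD of change is 0.775, so the standardised effect is 0.5/0.775 = 0.645. At two-sided 0.05 that gives about 73% power for the pre-post test and about 47% for the two-sample test of change. Adjusting the end score for baseline has residual SD √(1 − 0.7²) = 0.714 and gives about 53%. Part of the apparent advantage of the pre-post test is that it credits shared change to the intervention.

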Hypothesis #4: *Pre-post changes in UTBC factors will be related to increases in medication continuity.* We will calculate the change score for each relevant UTBC factor (end of study minus baseline) and the change score for medication continuity (percentage of days covered at end of study minus percentage of days covered in the 12 months prior to study). We will model the association between change in UTBC factor scores (independent variable) with change in medication continuity (dependent variable) using generalized linear mixed model. A significant effect of change in UTBC factor scores (beta coefficient) in the expected direction would indicate changes in UTBC factor scores were associated with medication continuity improvement.

Exploratory analyses:

We will conduct descriptive analyses to characterize rates of diversion at baseline and at the end of study using a McNemar's test to see if rates differ. We will summarize responses to the client satisfaction questionnaire descriptively as this may facilitate future dissemination.

Power and Sample Size:

The study would require a sample size of 18 for each group (i.e. a total sample size of 36), to achieve a power of 80% and a level of significance of .05 (two sided), to detect a difference in means between the intervention and the control groups of 15.7% (i.e. 66.2% vs. 50.5%) on the percentage of days covered with medicine assuming a pooled standard deviation of 16.5. Due to the low intra-class correlations observed in previous studies of ADHD medication continuity (ICC = 0; [name] et al. 2018), the analyses will not account for the nesting of patients within physicians. We will recruit 44 patients to ensure that 36 are retained at the end of the study. A retention rate of 80% (36/44) is conservative in light of the 12-month retention rate of 92% achieved by [name] in his current trial. We will use a stratified blocked randomization procedure to ensure baseline medication continuity is evenly distributed in both arms.

Scientific Rigor:

The RCT is a rigorous design to test efficacy of our intervention. We will explicitly address whether the intervention engages the mechanism underlying medication continuity and therefore warrants further testing in a future larger trial. Our preliminary data strongly supports the importance of the problem, intervention targets identified, and the feasibility of the approach in our hands.

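### Protocol Hypothesis 2 tests before-and-after scores of the same people without stating a within-person term; run as written, it loses power

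*Protocol*

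**What the plan says.** **Protocol, Data Analysis, Hypothesis #2.** The model class is given as follows: "Using a generalized linear model, we will test whether the intervention addressed the UTBC factors". The outcomes are the pre-intention scales and the adolescent and parent barrier scores. On the model's content: "Model predictors will include a fixed effect indicator of time point (baseline or end of study". The decision rule is: "A significant effect of time point in the expected direction would indicate UTBC factor improvement". No participant effect, GEE or paired structure is mentioned.

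**Protocol, Data Analysis, Hypothesis #4.** Each teen is first reduced to one continuity change score, "percentage of days covered at end of study minus percentage of days covered in the 12 months prior to study". Change in UTBC factors is then related to "change in medication continuity (dependent variable) using generalized linear mixed model". No random effect or grouping unit is named. The Power and Sample Size section adds that "the analyses will not account for the nesting of patients within physicians".

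**SAP (dated 12/15/2021; the protocol is dated 2/12/2021).** The opening paragraph says that results will be assessed as that document describes. Section 2.3.3 makes the per-person change the dependent variable for pre-intention factors, intention and both barrier scales. It compares change between arms and calls the test a paired t-test. It contains no single time-effect test and no analysis matching Hypothesis 4.

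**The concern.** Hypothesis 2 is decided by the significance of one coefficient, so the standard error of that coefficient settles the answer. Two scores from one person are usually positively correlated. A generalized linear model with time as its only term takes them as coming from different people and ignores that correlation. The protocol also uses the term generalized linear mixed model elsewhere, for Hypothesis 4. A programmer could therefore reasonably take the plain generalized linear model in Hypothesis 2 at face value.

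What is at stake is the mechanism claim. Under Scientific Rigor, the protocol says the trial will address whether the intervention engages the mechanism and so warrants a larger trial. A needlessly weak test could suggest that the mechanism was not engaged when it was.

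Hypothesis 4 raises a smaller question of the same kind: a mixed model is named where each teen contributes one outcome value.

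**Working it through.** **The plan's own figure.** The only computed design figure is for Hypothesis 3: difference 15.7, SD 16.5, two-sided alpha 0.05, power 80%. The normal formula gives n = 2(1.960 + 0.842)² × 16.5² / 15.7² = 17.3, so 18 per arm, as stated. Power from the noncentral t at 18 per arm is 79.2%. This reproduces and does not bear on Hypothesis 2, for which no effect size, SD, correlation or power is given.

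**Inputs for Hypothesis 2**
- n = 18: the planned number retained per arm (Power and Sample Size).
- r = 0.3, 0.5, 0.7: assumed pre-post correlation.
- True change of 0.5 SD, equal SD at both times, normal scores: assumed.
- One arm analysed: assumed. Hypothesis 2 does not say whether it is confined to the intervention arm.

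**Standard error of the time effect, in SD units.** The estimate is the same either way: mean at end minus mean at baseline.
- Records taken as independent: √(2/n) = √(2/18) = 0.333.
- Pairing respected: √(2(1−r)/n).
- Ratio: 1/√(1−r).

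| r | SE, independent | SE, paired | Ratio | Actual size of the 5% test, independent | Power, independent | Power, paired |
|---|---|---|---|---|---|---|
| 0.3 | 0.333 | 0.279 | 1.20 | 2.1% | 28% | 39% |
| 0.5 | 0.333 | 0.236 | 1.41 | 0.7% | 25% | 52% |
| 0.7 | 0.333 | 0.183 | 1.83 | 0.1% | 21% | 73% |

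Size and power for the independent analysis come from simulation. Paired power is from the noncentral t with 17 degrees of freedom and noncentrality 0.5√18/√(2(1−r)).

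**Sensitivity to n**, power at r = 0.3, 0.5 and 0.7:
- 22 (all enrolled in one arm, 44/2, no attrition): about 35, 32 and 29% independent, against 47, 61 and 82% paired.
- 36 (both arms pooled): about 56, 58 and 59%, against 69, 83 and 96%.

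The loss is present at each n.

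**Direction.** At r = 0 the two analyses agree. Only a negative correlation would make the independent test too liberal: at r = −0.2 the SE ratio is 0.91 and the actual size is 7.3% with n = 18. That is not the usual pattern for repeated scores on one scale.

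**Hypothesis 4.** With one normal outcome per teen and a participant intercept, the likelihood depends only on the sum of the two variances. In a simulated data set of 36 teens, the log-likelihood was −146.505 whether 0, 25, 50, 75 or 99% of the variance was given to the intercept. A trial mixed-model fit (in Python, not the SAS named in the SAP) split the variance in half, warned that the Hessian was not positive definite, and gave the slope 9.526 a standard error of 1.95. Ordinary regression gave the same slope with a standard error of 2.32. Stacking several factors, or teen and parent rows, does not help, because the outcome repeats on every row of a teen.

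**The case against.** The strongest reply is that the later SAP has overtaken the protocol model. It says that results follow the SAP, its per-person change scores already respect the pairing, and Hypothesis 4 does not appear there. Most of this stands: if only the SAP analyses are reported, the figures above describe a model that will not be run. It does not close the point. The SAP does not withdraw Hypothesis 2, and it gives no valid model for it, because a paired t-test cannot compare change between two independent arms.

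Second, saying that predictors will include time is not an exhaustive list and says nothing about covariance. A GEE or repeated-measures analysis may be intended. This also stands. A reader might infer that the Hypothesis 2 standard errors are certainly wrong. The text supports only that the within-person structure is unstated, and that the error follows if the model is run as written.

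Third, a reader might infer that the Hypothesis 4 model must fail, or that the two model classes were swapped by mistake. The documents do not support either. No random effect is named for Hypothesis 4. Without one, the model is ordinary regression. With a participant intercept, the slope is unaffected and only the variance split and the reported standard error are in doubt. A swap is conjecture.

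Fourth, the error is conservative and touches mechanism hypotheses only. That is correct, and it limits the weight of the point.

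**Conclusion.** The point holds in a limited form. The protocol does not state how Hypothesis 2 handles two records per person. If the records are treated as independent, the standard error is 1.20 to 1.83 times too large for r from 0.3 to 0.7. At n = 18, power for a 0.5 SD change falls from 39–73% to 28–21%. The correlation, the effect and the use of one arm are assumptions; the SE ratio depends only on the correlation, given equal SDs.

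A reader might infer a risk of false claims of improvement from this. With positive correlation the opposite holds: the 5% test runs at 2.1% or less.

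The two documents differ on how UTBC change is tested and need to be aligned. Hypothesis 4 is a minor point of model naming. Hypothesis 3, its sample size and the randomised comparison are unaffected.

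**What to change.** 1. **Hypothesis 2.** Wherever the time effect is reported, analyse the within-person change directly, or add a participant random intercept or a repeated-measures/GEE structure to the model. State which arm or arms are included.
2. **Alignment.** Have the SAP either restate Hypothesis 2 with that model or say that its change-score comparison replaces it. In the latter case, name a test for two independent groups in place of the paired t-test.
3. **Hypothesis 4.** If it is reported, name ordinary linear regression with one record per teen. If it is dropped, say so.

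The cost is a few sentences and about one line of code per model. No new data are needed, and the sample size does not change.

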#### 2.3.3 Secondary outcome analyses

- Change in pre-intention factors of Unified Theory of Behavior Change at baseline and approximately 4 months later.

The dependent variable will be the change in adolescent and parent self-report of pre-intention factors. Items were reported using a 5- or 7-point scale, depending on the item, which was then re-scaled to a 5-point scale for ease of interpretation. Differences in change score between intervention and control groups on this outcome will be evaluated using a Paired t-test.

- Change in intention to take/give ADHD medicine regularly at baseline and approximately 4 months later.

The dependent variable will be the change in the intention to take/give ADHD medicine. Items were reported using a 7-point scale, which were then re-scaled to be on a 5-point scale for ease of interpretation. Differences in change score between intervention and control groups on this outcome will be evaluated using a Paired t-test.

- Change in adolescent-report of medication barriers at baseline and approximately 4 months later.

The dependent variable will be the change in adolescent-report of medication barriers. Items were reverse coded so that higher scores mean less barriers. Differences in change score between intervention and control groups on this outcome will be evaluated using a Paired t-test.

- Change in parent-report of medication barriers at baseline and approximately 4 months later.

The dependent variable will be the change in parent-report of medication barriers. Items were reverse coded so that higher scores mean less barriers. Differences in change score between intervention and control groups on this outcome will be evaluated using a Paired t-test.

- Change in medication diversion at baseline and approximately 4 months later.

The dependent variable will be the change in medication diversion. Differences in change score between intervention and control groups on this outcome will be evaluated using a Paired t-test.

- Change in Decision Making Involvement Scale at baseline and approximately 4 months later.

The dependent variable will be the change in parent and adolescent-report of the Decision Making Involvement Scale subscale scores. Differences in change subscale score between intervention and control groups on this outcome will be evaluated using a Paired t-test.

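### Protocol Hypothesis 4 has no arm term and no stated population, and the SAP does not say whether it is kept; if both arms are pooled, the arm differences alone can produce the expected slope

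*Protocol*

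**What the plan says.** **Protocol, Data Analysis, Hypothesis #4.** Change scores are formed for UTBC factors (end of study minus baseline) and for coverage (end of study minus the preceding 12 months). Then: "We will model the association between change in UTBC factor scores (independent variable) with change in medication continuity (dependent variable"), by a generalized linear mixed model. The decision rule is: "A significant effect of change in UTBC factor scores (beta coefficient) in the expected direction would indicate changes in UTBC factor scores were associated" with better continuity. No other predictor is named, no random effect is named, and no population is given. Hypothesis #1, by contrast, fixes its population: "For each subject in the intervention group".

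**Purpose of the hypotheses.** The Data Analysis section opens: "Each hypothesis examines part of the mechanism underpinning intervention impact on medication continuity". Scientific Rigor adds: "We will explicitly address whether the intervention engages the mechanism underlying medication continuity and therefore warrants further testing in a future larger trial".

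**SAP.** Its introduction says: "The results of the Web Based Tools study will be assessed as described in this document". Section 1.1 has two working hypotheses, both between arms. The first is greater coverage in the intervention arm. The second reads: "compared to the control group, the intervention group will have improved outcomes as measured by change in the Unified Theory of Behavior Change factors". Section 2.3.3 plans only between-arm comparisons of UTBC change: "Differences in change score between intervention and control groups on this outcome will be evaluated using a Paired t-test". Sections 2.3.2 to 2.3.4 contain no model linking UTBC change to coverage and no statement that H4 is kept, replaced or dropped. The covariate rule in section 2.3.1 concerns imbalanced baseline characteristics in effectiveness analyses, so it does not supply an arm term for H4.

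**The concern.** The trial expects randomisation to the intervention to move both variables in H4, coverage and UTBC factors. Arm is therefore a planned common cause of the predictor and the outcome. If the arms are pooled without an arm term, the slope mixes two things: the difference between arms, and the association among adolescents within an arm. Only the second bears on whether those whose beliefs or barriers improved more were the ones whose coverage rose more.

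The design makes the distinction real, because its components act on different targets: videos on social norms, reminders on habits and environmental constraints. If reminders raised coverage while videos shifted norms, a pooled slope would tie norms to the coverage gain without any such link within arms.

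H4 is the only analysis in either document that relates the proposed mediators to coverage, so a reader would turn to it for that link.

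**Working it through.** **The plan's own figure.** Power and Sample Size gives 18 per group for 66.2% against 50.5% (15.7 points), SD 16.5, two-sided 0.05, 80% power. n = 2(1.960 + 0.842)² × 16.5² / 15.7² = 2 × 7.85 × 272.25 / 246.49 = 17.3, so 18 per group. Power at 18 is 81.4% (normal) or 79.2% (noncentral t). This reproduces. No figure is stated for H4.

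**Inputs for H4.** From the protocol: 18 per arm, 15.7 points, SD 16.5. Stratification on baseline coverage lets the planned difference carry over to the change score. Assumed, because the documents give no values:
- the arm shift d in UTBC change, 0 to 1.0 within-arm SD;
- the pre-post correlation r of coverage, 0.3 to 0.7, with equal SDs before and after. The change-score SD is 16.5 × √(2(1 − r)) = 19.5, 16.5 and 12.8 at r = 0.3, 0.5 and 0.7.

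There is one change score per patient and the protocol does not model clustering by physician, so the fixed part is fitted as ordinary least squares with one UTBC factor.

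**Pooled slope with no within-arm link.** With equal arms, the covariance is d × 15.7/4 and the variance of UTBC change is 1 + d²/4, so

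slope = (d × 15.7/4) / (1 + d²/4) points of coverage per within-arm SD of UTBC change.

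- d = 0.3: 1.1775/1.0225 = 1.15
- d = 0.5: 1.9625/1.0625 = 1.85
- d = 0.8: 3.14/1.16 = 2.71
- d = 1.0: 3.925/1.25 = 3.14

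Simulated means are slightly higher in this small sample: about 1.2, 1.9, 2.8 and 3.2.

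**Chance of a significant slope in the expected direction, no within-arm link** (two-sided p < 0.05, so nominal 2.5%; 40,000 runs per cell; ranges over r):

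| UTBC arm shift (SD) | Pooled, no arm term | With arm term |
|---|---|---|
| 0 | 2.4–2.6% | 2.4–2.6% |
| 0.3 | 5.1–6.7% | 2.4–2.6% |
| 0.5 | 7.7–11.2% | 2.4–2.6% |
| 0.8 | 12.4–20.7% | 2.4–2.6% |
| 1.0 | 16.8–28.9% | 2.4–2.6% |

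With an arm term the mean slope is about 0 in every cell. At half the planned coverage effect (7.85 points) the pooled rates run from about 4% at 0.3 SD to about 12% at 1.0 SD. If either arm difference is zero, the pooled slope averages 0 and the rate is nominal. Analysing the intervention arm alone also gives the nominal rate.

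**Direction.** The slope is positive for pre-intention scores and for barriers as reverse-coded in the SAP. As the protocol scores the barrier scales, higher means more barriers, so the same artefact is negative there, which is again the expected direction.

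**The case against.** **H4 may no longer be planned.** The SAP (12/15/2021) is later than the protocol (2/12/2021), says results are assessed as it describes, and restates only between-arm hypotheses. That H4 was superseded is a fair reading. This stands as a limit: the arm-term point applies only if H4 is kept. What remains either way is that the SAP does not say.

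**H4 may be meant for the intervention arm only.** H4 restricts itself to factors it calls relevant, which echoes the intervention-only Hypothesis #1 and the tailoring algorithm. Hypothesis #2, with only a time-point term, points the same way. In that case the problem does not arise. But the term is undefined for H4, so the population stays open.

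**H4 claims only association.** This stands. A reader might infer from the table that up to 29% of significant H4 results would be false. The documents do not support that: the rule concludes only that the changes were associated, and in a pooled sample they would be. The rates measure how often that association would appear with no within-arm link behind it. Engaging the mechanism may also mean no more than moving UTBC factors, which is Hypothesis #2 and SAP working hypothesis 2. The objection is only to reading the pooled slope as the mechanism link that the Data Analysis section says each hypothesis examines.

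**The size is driven by assumptions.** Also true. The rates above 12% require the full planned coverage effect and UTBC shifts of about 0.8 SD or more.

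**Conclusion.** The point holds conditionally and is minor. As written, H4 has no arm term and no population, and its status after the SAP is unstated. If it is kept and the arms are pooled, arm differences alone give about 5% to 29% significant slopes in the expected direction against 2.5%, or about 4% to 12% at half the planned coverage effect. These ranges rest on assumed UTBC shifts of 0.3 to 1.0 SD and pre-post correlations of 0.3 to 0.7.

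Two stronger readings should be resisted. First, that an arm term would make H4 a test of mediation. It removes one known confounder only. UTBC change is not randomised, and SAP sections 1.2 and 1.4 have coverage accruing over the four months that end with the follow-up survey, so taking medicine may have changed beliefs rather than the reverse, and other common causes remain. Second, that the trial's main result is in doubt. Hypothesis #3, its t-test and the sample size are untouched.

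**What to change.** 1. State in the SAP whether H4 is retained and, if so, in which participants.
2. If it is retained on both arms, add randomised arm as a fixed effect, keep the change-score outcome, and report the arm-adjusted slope as the H4 result. Show any slope without arm as description only.
3. Describe the arm-adjusted slope as a within-arm association consistent with the proposed mechanism, not as proof of it.
4. If H4 is dropped, say so, and label any later analysis of UTBC change against coverage as post hoc.

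**Cost.** SAP wording, one degree of freedom, and an assumed common slope in the two arms. At UTBC shifts of 0.3 to 1.0 SD the slope's standard error changes by about −13% (2.22 against 2.54) to +7% (3.39 against 3.17). There will be fewer significant slopes because the arm component is removed. With an assumed true within-arm correlation of 0.3, the rate is 42% against 51–84% pooled; with 0.5, it is 88% against 89–99%. Restricting to the intervention arm (n = 18) also avoids the problem but gives only 23% and 59%.
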